- b. Participants who prematurely discontinue study intervention for any reason (except withdrawal of consent) will be asked to continue with their remaining study visits and assessment schedule. Participants who withdraw consent during the treatment or follow-up phase will be offered an optional Early Exit Visit. The optional Early Exit Visit will occur the day of consent withdrawal or as soon as possible thereafter.
- c. Participants may initially sign a pre-screening ICF to allow for ambulatory NS1 rapid testing performed by a member of the mobile clinical team as a part of the recruitment strategy.
- d. Must be signed before first study-related activity.
- e. COVID-19 testing can be performed at the discretion of the investigator, depending on the epidemiological situation.

- f. Investigators should ensure that all study enrollment criteria have been met at screening.
- g. Calculated by the Modification of Diet in Renal Disease (MDRD) formula.
- h. Only for women of childbearing potential. Additional serum pregnancy tests may be performed, as determined necessary by the investigator or required by local regulation, to establish the absence of pregnancy at any time during the participation in the study.
- i. An NS1 rapid test can be performed ambulatory by a mobile clinical team member during pre-screening. Any participant who does not have a documented proof of a positive NS1 test performed by a doctor or by a mobile clinical team member prior to presenting himself/herself at the study site, will undergo an NS1 rapid test at screening.
- j. CCI

- k.
- l. A complete physical examination will be done at screening and at Day 28. At Days 3, 6, 14, and 21, a brief physical examination will be performed. At Days 1, 2, 4, 5, 7, 8, and 9, a physical examination may be performed at the investigator's discretion.
- m. Blood pressure, pulse rate, oxygen saturation (spO2) & input-output (I/O) will be measured every 6 hours during inpatient stay and once daily in case of ambulatory visits. Systolic and diastolic blood pressure and pulse/heart rate will be measured supine after at least 5 minutes rest. I/O ratio and spO2 will not be measured at screening.
- n. Two-hourly temperature monitoring during inpatient stay, starting at 6 AM in the morning (temperature will not be measured between midnight and 6 AM the next day. In case of ambulatory visits, temperature monitoring will take place once daily.

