4. STUDY DESIGN

4.1. Overall Design

This is a randomized, double-blind, placebo-controlled, multicenter, Phase 2a interventional study in participants aged ≥ 18 or ≥ 21 (depending on the legal age of consent in the jurisdiction in which the study is taking place) to ≤ 60 years. Participants who report with an onset of fever of < 48 -hour duration at screening, and who test positive for DENV infection by the NS1 assay will be randomized into the study. Randomization will be stratified by country and by duration of dengue symptoms from onset until the time of randomization (≤ 24 hours and > 24 hours).

The population will include participants with a primary and a non-primary or secondary infection. The difference between the 2 subpopulations will be determined before data base lock and will be based on the IgG profile.

A planned target of 150 male and female participants will be randomly assigned in a ratio of 1:1 to receive JNJ-64281802 or placebo in this study with approximately 75 participants planned per intervention group. The sample size can be revised after an interim analysis on the proportion of primary versus secondary DENV infections (refer to Section 9.5, Interim Analysis).

There are three sequential phases in the study: screening/baseline, double-blind treatment and follow-up. Study participants will complete the screening/baseline visit on Day 0 (predose), followed by a double-blind treatment phase from Day 1 to Day 6 or Day 9 (for participants with dengue warning symptoms). During the double-blind treatment phase, the participants will be admitted to an inpatient facility. At the investigator's discretion, ambulatory visits instead of inpatient treatment can be allowed at Days 3, 4, 5, and 6. All participants will be followed up for a total of 6 months after the first dosing day. The entire study duration for each participant will be approximately 6 months (± 4 days). The participants will complete the study after having completed the final remote follow-up assessment planned 6 months (± 4 days) after having received the first dose of study intervention, unless ongoing adverse events (AEs) require monitoring.

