Mobile clinical teams consisting of trained and delegated site staff (eg, nurses, clinical research coordinators [CRCs]) will visit the clinics and communities to sensitize and pre-screen potential study participants and will play an active role in participant recruitment. Individuals with a suspected DENV infection will be asked to undergo an NS1 rapid test after signing a pre-screening ICF during an ambulatory visit at a health care facility organized by the mobile clinical teams.

The study sites will be open to receive referrals of participants who have consulted a health care facility (eg, clinic/polyclinic, hospital) or practitioner (eg, general practitioner [GP], medical

doctor [MD], nurse) with an onset of fever within the last 48 hours, as reported by the participant, and who tested positive for DENV infection by the NS1 assay at the health care facility. Individuals who test positive during an ambulatory visit or as part of Standard of Care DENV NS1 rapid testing, will be referred to the study site to further coordinate informed consent signing and completion of eligibility assessments. In addition, participants may also report directly to the study site. Participants identified at the study site with an onset of fever as reported by the participant within the last 48 hours, and who test positive for DENV infection by the NS1 assay performed at the site after signing the ICF, will undergo eligibility assessments.

The screening/baseline assessments are to be completed as quickly as possible at the study site. Participants who successfully meet all inclusion criteria and none of the exclusion criteria, will be enrolled and admitted to an inpatient facility. The participants will then be randomized to receive placebo or JNJ-64281802. CCI

Results of screening assessments need to be documented in the electronic case report form (eCRF).

Placebo or JNJ-64281802 will be administered on Days 1 to 5, starting from the day of randomization (Day 1). The participants will stay at the inpatient facility from Day 1 to Day 6 (with an option to attend ambulatory visits on Days 3, 4, 5, and 6 instead at the investigator's discretion) and daily clinical monitoring will be conducted, and blood samples will be collected as shown in [Schedule of Activities](#). Oral intake of food and fluids will be recorded on Days 1, 2, 3, 4, and 5 of dosing.

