7. DISCONTINUATION OF STUDY INTERVENTION AND PARTICIPANT DISCONTINUATION/WITHDRAWAL

7.1. Discontinuation of Study Intervention

A participant's study intervention must be discontinued if:

- The participant withdraws consent to receive study intervention
- The investigator believes that for safety reasons or tolerability reasons (eg, an AE) it is in the best interest of the participant to discontinue study intervention
- The participant becomes pregnant

If a participant discontinues study intervention for any reason (except withdrawal of consent) before the end of the double-blind treatment phase, the participant will be asked to continue with their remaining study visits and assessment schedule. Participants who withdraw consent during the treatment or follow-up phase, will be offered an optional Early Exit Visit. The optional Early Exit Visit will occur on the day of consent withdrawal or as soon as possible thereafter and will consist of the same assessments as at the Day 28 follow-up visit.

Additional participants may be entered only for those participants who discontinued study drug before last dose of study drug on Day 2 to ensure the protocol-specified number of participants complete the study.

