| 
Grade 3 rash^b
 
Diffuse rash AND vesicles or limited number of bullae or superficial ulcerations of mucous membrane limited to 1 site,
 
OR elevations in AST/ALT >2x ULN,
 
OR body temperature $\geq 39.3^{\circ}\text{C}$ to $<40.0^{\circ}\text{C}$ ($\geq 102.7^{\circ}\text{F}$ to $<104.0^{\circ}\text{F}$),
 
OR eosinophils $>1000/\text{mm}^3$,
 
OR serum sickness-like reaction.
 | 
Must permanently discontinue and be withdrawn from the study; no rechallenge allowed.
 | 
Day 0: required on-site unscheduled visit for initial rash evaluation, if participant is outside the study site.
 
Day 0 and 1:
 
 • Safety laboratory assessments are required. • Digital pictures^d of skin lesions should be taken within 24 hours after the onset of the rash and on Day 1. 
Further visit(s): appropriate management and follow-up required until resolution of rash or until clinical stability is reached.
 
Days 2, 3, and 4: Only if the participant's AST/ALT on Day 0 and/or Day 1 of rash $>2x$ ULN and/or in case of rash progression:
 
 • Additional safety blood samples are required. • Digital pictures^d are to be taken. 
Day 5: Regardless of the Day 0/1 AST/ALT levels or rash progression:
 
 • Additional safety blood samples are required. • Digital pictures^d are to be taken. 
After Day 5: Weekly follow-up visits are required (or more frequently at the investigator's discretion) as long as Grade 3-4 rash is present. Once Grade 3-4 rash has resolved to \leqGrade 2 rash, follow-up should be done according to the instructions for follow-up visits for Grade 1 or Grade 2 rash, respectively.
 
 • Only if the participant's AST/ALT on Day 5 of rash is still $>2x$ ULN and/or in case of rash progression, additional safety blood samples and digital pictures^d are required at these weekly follow-up visits, until resolution or stabilization of the AST/ALT elevations. 
Upon resolution/stabilization of the rash: digital pictures^d should be taken and the final rash assessment pages of the eCRF should be completed.
 | 
Required^c
 
Biopsy required within 24hrs after onset of rash.
 |

| Definition | Study Drug Action | Activities by Day ^a | Referral to Dermatologist and Dermatology Activities | |

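### For a drug-suspected Grade 3 or 4 rash during dosing, Table 4 orders withdrawal from the study while Section 7.1 asks for visits to continue (minor).

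*Protocol*

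**What the plan says.** **The rash rule.** Appendix 7 (Section 10.7) applies when a causal role for study drug cannot be ruled out. In Table 4, under the column for study drug action, the Grade 3 and Grade 4 rows carry the same instruction: "Must permanently discontinue and be withdrawn from the study; no rechallenge allowed". The same rows require rash visits, blood tests, photographs and dermatology referral.

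**The general rule.** Section 7.1 gives three grounds on which drug must be stopped. One reads: "The investigator believes that for safety reasons or tolerability reasons (eg, an AE) it is in the best interest of the participant to discontinue" the intervention. For any stop other than withdrawal of consent that occurs "before the end of the double-blind treatment phase, the participant will be asked to continue with their remaining study visits and assessment schedule". Footnote b of the Schedule of Activities says the same: "Participants who prematurely discontinue study intervention for any reason (except withdrawal of consent) will be asked to continue with their remaining study visits". Sections 4.1 and 4.4 repeat it.

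**Leaving the study.** Section 7.2 lists loss to follow-up, withdrawal of consent and death. On exit assessments, Section 7.1 says: "Participants who withdraw consent during the treatment or follow-up phase, will be offered an optional Early Exit Visit". On replacement it says: "Additional participants may be entered only for those participants who discontinued study drug before last dose of study drug on Day 2".

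**The concern.** A site that sees a qualifying rash on Days 1 to 5 cannot follow both instructions. One removes the participant from the study. The other keeps the participant on the visit schedule.

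The dosing window is also the window of the primary endpoint, the area under the log10 viral-load curve from baseline to Day 5. If the participant is withdrawn before the Day 5 sample, the curve is cut short for a reason that may be related to treatment. Section 9.4.2.1 gives no rule for an incomplete curve. A participant who stops after the last Day 2 dose may not be replaced.

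Scheduled safety follow-up unrelated to the rash would also end, although drug is still present: Section 2.2 reports a half-life of 6.3 to 9.2 days. No exit visit is named for someone withdrawn because of rash.

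**Working it through.** The plan states no figure to reproduce here. The check compares the texts and then counts scheduled contacts.

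**1. Do both rules apply to the same participant?** Dosing runs from Day 1 to Day 5 (Section 4.1). The double-blind phase runs to Day 6, or to Day 9 with warning symptoms. A stop for rash on Days 1 to 5 is a stop for an adverse event before that phase ends. It therefore meets both the Section 7.1 condition and Table 4.

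**2. Does any text settle the order?**

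| Text | What it implies |
|---|---|
| Section 7.1; repeated in 1.3 footnote b, 4.1 and 4.4 | Continue visits; the only exception is withdrawal of consent |
| Section 7.2 list | Rash is not a listed reason for leaving the study |
| Section 8.3.5 | Pregnancy, another mandatory drug stop, keeps the participant in the study |
| Section 2.3.4 | Describes Appendix 7 as extra safety follow-up; silent on withdrawal |
| Section 9.4.5 and Appendix 9 | Contemplate leaving the study because of an adverse event |

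None of these gives precedence to either rule.

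**3. What about a rash after the treatment phase?** The Section 7.1 sentence no longer applies. The remaining tension is with the Section 7.2 list. The statement in Section 4.1 that "All participants will be followed up for a total of 6 months after the first dosing day" is general, and every permitted withdrawal departs from it, so it adds little.

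**4. What would be lost, if withdrawal ends scheduled visits?**

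- On-site assessments after Day 5 on the standard schedule: Days 6, 14, 21 and 28, which is 4.
- Remote contacts every 14 days after Day 28: Days 42, 56, 70, 84, 98, 112, 126, 140, 154, 168 and 182, which is 11. Equivalently, (182 − 28)/14 = 11. Taking six months as 180 to 184 days (an assumption), Day 182 lies within 2 days of either end, inside the ±4-day window of the required final contact.

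| Time of withdrawal | Primary AUC | Scheduled contacts lost |
|---|---|---|
| Before the Day 5 sample | Truncated | Remaining samples to Day 5, then 4 + 11 = 15 |
| After Day 6, before Day 14 | Complete | 3 + 11 = 14 |
| After Day 28 | Complete | Remaining remote contacts, at most 11 |

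The counts leave out Days 7 to 9, which apply only to an extended stay.

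**5. What would continue?** Table 4 rash visits continue, as does follow-up of persisting clinically significant abnormalities (Section 8.2) and of unresolved serious adverse events (Appendix 4). The rash blood tests cover liver enzymes, creatinine, sedimentation rate and blood count. They do not include viral load, so they do not fill the gap in the AUC.

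**6. How often?** No rate can be derived. Section 2.2 reports two drug-related rashes in Phase 1, both Grade 2, with onset on dosing Days 10 and 13. Neither met the grade trigger, and neither began within five days of dosing. Against that, on the natural reading of the Grade 3 definition, AST/ALT above twice the upper limit or a temperature of 39.3 to below 40.0 °C can raise a diffuse rash to Grade 3. Recent fever is an entry criterion, and liver enzymes exclude only above 1000 U/L. Appendix 7 also accepts that dengue rash and drug rash may be indistinguishable.

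**The case against.** The strongest reply is that the loss of data depends on a reading. No text defines what withdrawal other than withdrawal of consent brings to an end, and Section 7.2 bars further assessments only after consent is withdrawn. The Table 4 phrase stands in a column about study drug, next to compulsory later visits, so it may be loose wording for stopping the drug. This stands as a limit: the 15 contacts are what is lost under the ordinary meaning of *withdrawn*. It does not remove the conflict, because the cell as written says more than stop the drug.

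It can also be said that a specific *must* outranks a general request to continue. That is arguable, but Section 7.1 names its one exception and rash is not it.

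The event is probably rare, the sample size already allows about 4% drop-out for other reasons (Section 9.2), and very early stops can be replaced. All of this stands and keeps the point minor.

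A reader might go further in three ways that the documents do not support:

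- **That safety follow-up ceases altogether, or that Table 4 contradicts itself by ordering visits after withdrawal.** Rash visits and follow-up of unresolved events are compatible with withdrawal for a reason other than consent.
- **That the protocol never allows withdrawal for an adverse event.** Section 9.4.5 and Appendix 9 both contemplate it.
- **That the primary comparison is biased.** No rate, no difference between arms and no size of bias can be obtained from the documents.

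**Conclusion.** The conflict is real, and the protocol is wrong as written on this point, but the matter is minor. For a drug-suspected Grade 3 or 4 rash during dosing, two current instructions are incompatible and neither is given precedence. The effect per affected participant is a truncated primary AUC if withdrawal precedes the Day 5 sample, and up to 15 later scheduled contacts on the standard schedule. That size rests on *withdrawn* having its ordinary meaning and on six months being 180 to 184 days. The effect on the trial as a whole cannot be computed and is probably small. No reported result changes: SAP Sections 1 and 1.1 record closure with five participants and no formal analysis of the objectives.

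**What to change.** In the Grade 3 and Grade 4 study-drug-action cells of Table 4, replace the present instruction with: *Study drug must be stopped permanently and not restarted. The participant will be asked to keep to scheduled visits and assessments under Section 7.1, including viral-load sampling through Day 5, as clinically feasible, in addition to the rash visits in this table.*

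The drug-stopping rule is unchanged, and the qualifier leaves room for a participant too ill to attend. Naming Grade 3 or 4 rash as an exception in Sections 7.1 and 7.2 would also remove the clash, but it would give up the Day 1 to 5 samples and the scheduled follow-up, so retention is preferable. The cost is wording in two cells, with no visits beyond those already in the Schedule of Activities and Table 4. The amendment history gives alignment between studies as the reason for adding the updated rash section, so other protocols that use it should be checked for the same wording.

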10.8. Appendix 8: Protocol Amendment History

The Protocol Amendment Summary of Changes Table for the current amendment is located directly before the Table of Contents (TOC).

Amendment 5 (28 February 2022)**Overall Rationale for the Amendment:** CCI

In addition, CCI to increase the upper age limit to 60 years of age, to relax the restrictions on the use of CYP3A4 and UGT1A9 inhibitors, to remove the restrictions on the use of substrates for CYP2C9 or CYP2C19, to reschedule the interim analysis at the originally planned time point and to add a primary analysis.

Some minor corrections and/or clarifications were addressed as outlined in the table below.

| Section number and Name | Description of Change | Brief Rationale |
|--|---|--|
| 1.1 Synopsis 1.3 Schedule of Activities 4.1 Overall Design 5.3.1 Meals and Dietary Restrictions 6.1 Study Intervention(s) Administered | CCI | To facilitate cultural and operational aspects of the study and to protect the safety of the participants. |
| 1.1 Synopsis 1.3 Schedule of Activities 4.1 Overall Design 5. Study Population 5.1 Inclusion Criteria 6.1 Study Intervention(s) Administered 6.3 Measures to Minimize Bias: Randomization and Blinding | The time window of 12 hours between signing ICF and receiving the first dose of study intervention has been removed. Following criteria have been added: 
 Participants must be identified and screened within 48 hours after onset of fever. CCI | To accommodate the investigator's request. |
| 1.1 Synopsis 4.1 Overall Design 5.1 Inclusion Criteria | The upper age limit for inclusion in the study has been increased to 60 years of age. | To accommodate the investigator's request to be able to include older patients. |
| 2.2 Background 5.2 Exclusion Criteria 6.5 Concomitant Therapy | The restriction on the use of CYP3A4 and UGT1A9 inhibitors has been relaxed to 'within 7 days before first dose of study drug'. Restrictions on the use of substrates for CYP2C9 or CYP2C19 have been removed. | Based on available clinical drug-drug interaction study data, restrictions on concomitant medications have been relaxed. |

| Section number and Name | Description of Change | Brief Rationale |
|---|--|---|
| 1.1 Synopsis 1.3 Schedule of Activities 8. Study Assessments and Procedures 8.2.1 Physical Examinations 9.4.4 Immune Analysis | 
The SoA has been updated:
 
 Physical examination during inpatient stay will occur only at screening, Day 3 and Day 6. On the other dosing days, physical examination will be performed ad hoc at the discretion of the principal investigator. Physical examination during the follow-up visits (Days 14, 21, and 28) remains as is. A clinical status check prior to the first dosing has been added. Safety laboratory tests have been added on Day 6, at the discretion of the investigator. 
The blood volume that needs to be collected for the safety laboratory tests as well as the total blood volume for the study have been updated.
 | To monitor the safety of the study participants. |
| 1.1 Synopsis 4.1 Overall Design 6.3 Measures to Minimize Bias: Randomization and Blinding 9.4.1 General Considerations 9.5 Interim Analysis | 
The section 'Interim Analysis' has been updated to reschedule the interim analysis at the originally planned time point when at least 50 participants with a primary dengue infection reached Day 28 or discontinued earlier.
 
A primary analysis has been added at the time point when all participants reached Day 28 or discontinued earlier.
 
During this interim and primary analyses, the database will remain blinded to the site personnel to ensure that the 6-months safety follow-up can be performed in a blinded fashion.
 | 
The time point of the interim analysis has been rescheduled to the originally planned time point when at least 50 participants with a primary dengue infection reached Day 28 or discontinued earlier.
 
A primary analysis has been added to provide the originally planned 'final analysis' when all participants reached Day 28 or discontinued earlier.
 |
| 10.7 Appendix 7: Rash Management | The 'Rash Management' appendix has been updated to ensure that only if causal relationship is considered, a rash management should be started. The Day 7 visit and assessments in case of Grade 1 rash have been removed. | Majority of participants will present with a typical dengue-related rash to requiring initiation of the rash management. From safety perspective and to facilitate operational conduct of the study, duration to follow-up Grade 1 rash was reduced. |
| 1.3 Schedule of Activities | The blood sample collection for cellular immunity (PBMC) has been made optional at Day 28. | To accommodate the investigator's request to reduce the total blood volume at Day 28. |
| 1.1 Synopsis 3. Objectives and Endpoints | 
Two exploratory objectives have been updated:
 
 Investigate the antiviral activity of JNJ-64281802 versus placebo in terms of reduction of DENV RNA in secondary DENV infections and in all DENV infections Investigate the antiviral activity of JNJ-64281802 versus placebo based on viremia in secondary DENV infections and in all DENV infections | Clarification of the objectives. |
| 9.4.5 Pharmacokinetic Analyses | Additional wording was added to ensure that PK samples collected before a certain date will be included in a population PK analysis. | To analyze the PK profile early in the study. |

| Section number and Name | Description of Change | Brief Rationale |
|--|---|--|
| 1.1 Synopsis 1.3 Schedule of Activities 4.1 Overall Design 6.1 Study Intervention(s) Administered | CCI | Correction. |
| 2.2 Background | The clinical background section has been updated to include studies DNG1006 (food effect), DNG1004 (drug-drug interaction) and DNG1005 (drug-drug interaction). | For completeness. |
| 1.1 Synopsis 1.3 Schedule of Activities 4.1 Overall Design 4.4 End of Study Definition | It has been clarified that participants will be followed up remotely until 6 months after the first dose of study intervention. | Clarification of total study duration. |
| 1.3 Schedule of Activities | It has been clarified that the time window for the study assessments is ± 30 min for the assessments at Days 1 to 3 and ± 2 hours for the assessments at Days 4 and 5. | For completeness. |
| 8.3.5 Pregnancy | The wording 'and any postnatal sequelae in the infant' has been removed from the below sentence: Follow-up information regarding the outcome of the pregnancy and any postnatal sequelae in the infant will be required. | Correction. The Sponsor follows-up on pregnancy through birth and status of newborn, but no additional follow-up is required, unless safety issues are reported. |
| Throughout the protocol | Minor updates, corrections, or additions have been made. | Correction, clarification, and consistency. |

Amendment 4 (22 November 2021)

Overall Rationale for the Amendment: The protocol was amended to reflect new strategies to expedite participant enrollment, to disallow the use of UGT1A9 inhibitors or inducers before and during the study, to accommodate COVID-19 vaccination strategies, and to extend the follow-up period until 6 months post dosing. In addition, some minor corrections and/or clarifications were addressed as outlined in the table below.

| Section number and Name | Description of Change | Brief Rationale |
|--|---|---|
| 1.1 Synopsis 1.3 Schedule of Activities 4.1 Overall Design 5.1 Inclusion Criteria 10.3 Appendix 3: Regulatory, Ethical, and Study Oversight Considerations | Individuals with a suspected dengue virus infection will be asked to undergo an NS1 rapid test under a pre-screening consent during an ambulatory visit organized by the mobile clinical team. Patients who test positive for dengue virus infection will be subsequently referred to the study site. | A broader and more pro-active strategy for participant recruitment will be implemented in order to expedite study enrollment. |
| 5.2 Exclusion Criteria 6.5 Concomitant Therapy | The use of UGT1A9 inhibitors or inducers within 14 days before the first dose of study drug is not permitted. | JNJ-64281802 is a substrate for UGT1A9 based on in vitro results. A possible drug-drug interaction cannot be excluded at this time. |

| Section number and Name | Description of Change | Brief Rationale |
|---|---|--|
| 1.3 Schedule of Activities 2.3.4 Potential Risks 5.2 Exclusion Criteria 6.5 Concomitant Therapy 10.9 Appendix 9: COVID-19 Appendix | An authorized/licensed COVID-19 vaccine can be administered at any time before, during, or after the study. COVID-19 testing can be added as a screening assessment at the discretion of the investigator, depending on the epidemiological situation. The COVID-19 appendix has been updated and aligned with other dengue clinical study protocols. Other concomitant vaccinations are not allowed until 30 days after the last dose of study drug, where the period was reduced from 90 to 30 days. | To accommodate COVID-19 vaccination strategies and for alignment within the dengue study program. No substantial accumulation of the compound is expected in the treatment study. |
| 1.1 Synopsis 1.3 Schedule of Activities 4.1 Overall Design 4.4 End of Study Definition 7.1 Discontinuation of Study Intervention 8.2.1 Physical Examinations 9.4.4.2 Cellular Immune Analyses | Remote every-2-weeks follow-up visits until 6 months after the last dosing day have been added to inquire on any dengue-related signs and symptoms. A distinction between on site (ie, on Days 14, 21, and 28) and remote (ie, every-2-weeks after Day 28 and until 6 months after the last dosing day) follow-up visits was made. As a result, participants will only have completed the study after the final remote follow-up assessment at Mont 6 post dosing. | To accommodate the investigator's request for a longer follow-up period. |
| 1.1 Synopsis 1.3 Schedule of Activities 8.3.2 Method of Detecting Adverse Events and Serious Adverse Events 10.2 Appendix 2: Clinical Laboratory Tests | International normalized ratio (INR) has been specified as an additional parameter in blood coagulation assessments. | The INR is an international standard for the prothrombin time (PT). |
| 1.1 Synopsis 1.3 Schedule of Activities 1.2 Schema 4.1 Overall Design | For eligibility and screening assessments, participants will be directed to the study site. During the treatment phase, participants will be admitted to an inpatient facility. Participants with symptoms of severe dengue or with dengue warning symptoms, will be transferred to a hospital. | To accommodate the site's request to allow for flexibility on where the participant will be admitted. To allow for flexibility on where the participant will be hospitalized. |
| 1.3 Schedule of Activities 8 STUDY ASSESSMENTS AND PROCEDURES | It was emphasized that for all assessments the 30-minute time window as defined in the schedule of activities should be adhered to. | Clarification requested by the study site. |
| 8 STUDY ASSESSMENTS AND PROCEDURES | The blood volume that needs to be collected for each of the assessments has been updated. | For alignment and consistency with laboratory manual and on-site practices. |

| Section number and Name | Description of Change | Brief Rationale |
|--|--|---|
| 1.1 Synopsis 4.1 Overall Design 8 STUDY ASSESSMENTS AND PROCEDURES 8.1 Antiviral activity Assessments | Samples that tested positive for NS1 rapid test will no longer have to be confirmed by a qualitative PCR at screening. | To expedite screening assessments and start of treatment. |
| 1.1 Synopsis 1.3 Schedule of Activities 4.1 Overall Design 6.1 Study Intervention(s) Administered | CCI | Clarification requested by the study site. |
| 1.1 Synopsis 1.2 Schema 1.3 Schedule of Activities 4.1 Overall Design | It was emphasized that participants with signs and symptoms of severe dengue can be transferred to a hospital at any time during the study and at the investigator's discretion. Participants with severe dengue OR dengue warning symptoms after Study Day 9 will also be moved to a hospital. | Clarification requested by the study site. |
| 1.1 Synopsis 9.4.2 Antiviral Activity Analysis | Viral load assay results below the limit of detection (LOD) will be described as target not detected. | To align with the data transfer agreement. |
| 1.3 Schedule of Activities | Review of concomitant medication and adverse events were indicated as 'continuously' in the Schedule of Activities. | Clarification as these are being reported on occurrence. |
| 1.1 Synopsis 1.3 Schedule of Activities 2.2 Background 4.1 Overall Design 5.3.1 Meals and Dietary Restrictions 6.1 Study Intervention(s) Administered | CCI | Correction and clarification. |
| 1.3 Schedule of Activities 5.2 Exclusion Criteria 8.2.2 Vital Signs | Oxygen saturation has been removed as a screening assessment and will be measured pre-dose on Day 1 (vital signs). | Correction, clarification, and consistency. |
| 10.2 Appendix 2: Clinical Laboratory Tests | Indirect bilirubin has been removed from the safety laboratory assessments. | Local laboratory cannot provide this test. |
| 8.3.5 Pregnancy | Participants becoming pregnant during the study will discontinue study intervention but will continue study visits for additional safety follow-up. | Correction, clarification, and consistency. |
| 1.3 Schedule of Activities | One line for blood sample collection for NS1 concentration was removed from the schedule of activities. | Correction, as the assessment was duplicated. |
| 10.7 Appendix 7: Rash Management | The word 'asymptomatic' has been removed to describe a Grade 1 rash. | To align wording across studies. |

| Section number and Name | Description of Change | Brief Rationale |
|------------------------------------|--|--|
| 1.1 Synopsis 4.1 Overall Design | Screening and baseline assessments are completed on Day 0. | Correction to align with the Schedule of Activities. |
| Throughout the protocol | Minor updates, corrections, or additions have been made. | Correction, clarification, and consistency. |

Amendment 3 (26 March 2021)

Overall Rationale for the Amendment: The protocol was amended as specified below.

| Section number and Name | Description of Change | Brief Rationale |
|--|--|--|
| 1.1 Synopsis 1.3 Schedule of Activities 2.2 Background 4.1 Overall Design 5.3.1 Meals and Dietary Restrictions 6.1 Study Intervention(s) Administered | CCI | To facilitate cultural and operational aspects of the study. |
| 1.1 Synopsis 1.3 Schedule of Activities 4.1 Overall Design | CCI | To offer additional guidance to the study site. |
| 1.3 Schedule of Activities | Guidance on the allowed blood sampling time window was added to the schedule of activities. | To offer additional guidance to the study site. |
| 1.1 Synopsis 4.1 Overall Design 9.5 Interim Analysis | Sentence was added with regards to treatment effect and the futility stopping boundary at the time of the interim analysis. | To get a better understanding of how different the observed versus the assumed effect can be, in order to make a well-informed sponsor decision at the time of the interim analysis. |
| 1.1 Synopsis 5.1 Inclusion Criteria 7.2.1 Withdrawal from the Use of Research Samples 8 STUDY ASSESSMENTS AND PROCEDURES 8.6.1 Human Leucocyte Antigen Typing and Pharmacogenomics Assessments 10.3 Appendix 3: Regulatory, Ethical, and Study Oversight Considerations | Because human leukocyte antigen (HLA) and pharmacogenomic samples are required, the word 'optional' was removed. Where local regulations require, a separate consent can be obtained for this part of the study. The use of leftover samples for future exploratory research is optional and will be consented separately in the informed consent form (ICF). | Clarification and correction of inconsistencies. |
| 2.2 Background 2.3.4 Potential Risks | Information on cardiovascular safety was removed from potential risks. Instead, a paragraph on exposure analysis was added to the overall safety data. | Cardiovascular safety is not considered to be a potential risk. |

| Section number and Name | Description of Change | Brief Rationale |
|--|---|--|
| 1.3 Schedule of Activities 8.2.2 Vital Signs | Input-Output (I/O) ratio will be measured from predose till discharge, not during screening. | Correction of errors and inconsistencies. |
| 1.1 Synopsis 1.2 Schema 4.1 Overall Design 10.1 Appendix 1: Abbreviations | Participants with severe dengue after Day 9 will be transferred to the Singapore General Hospital (SGH), and not to the National University Hospital. In addition, at the investigator's discretion, participants who are hemodynamically unstable or require interventions, can be transferred to the SGH anytime during the inpatient stay at the investigational medicine unit (IMU). | Updates made based on site-specific input. |
| 1.2 Schema 1.3 Schedule of Activities 10.9 Appendix 9: COVID-19 Appendix | Hospitalization at the SingHealth investigational medicine unit (IMU) has been replaced with inpatient stay at IMU. | Update in terminology to make a clear distinction between inpatient stay at IMU during treatment and transfer to the hospital for participants with severe dengue. |
| 1.1 Synopsis 4.1 Overall Design 5.1 Inclusion Criteria 10.1 Appendix 1: Abbreviations | The terminology healthcare clinics (HCCs) was changed to general practitioner clinics (GP) throughout the document. | Correction of errors and inconsistencies. |
| 8.3.4 Regulatory Reporting Requirements for Serious Adverse Events | Anticipated events and Anticipated Events Safety Monitoring Plan were removed, because they are not applicable for this study. | Correction of errors and inconsistencies. |
| 8.5.3 Pharmacokinetic Parameters and Evaluations | Plasma protein binding was replaced with 'protein binding' with regards to Alpha-1 acid glycoprotein, because this is detected in serum not plasma. | Correction of errors and inconsistencies. |
| 10.2 Appendix 2: Clinical Laboratory Tests | C-reactive protein was added to the biochemistry assessments. | Clarification. |
| 4.1 Overall Design 10.3 Appendix 3: Regulatory, Ethical, and Study Oversight Considerations | It was clarified that the data review committee (DRC) will be consulted in case of significant or unexpected safety events and for quarterly (or when 50 new participants are enrolled, whichever comes first) safety analyses. | Clarification. |
| 2.3.4 Potential Risks 5.2 Exclusion Criteria 6.5 Concomitant Therapy | COVID-19 vaccination was added as an exception to be allowed as concomitant vaccination 30 days after the last dosing. | To accommodate for COVID-19 vaccinations during the pandemic. |
| 1.1 Synopsis 4.1 Overall Design | Follow-up period has been corrected to 23 days (± 2 days) after the last dosing day. | Alignment with the SoA. |
